mindfulness (13, 14), stress symptoms (14, 15), emotion regulation (16), and quality of life and general health (15, 17) in Western and Asian countries. However, no study has examined the effectiveness of mindfulness-based interventions among ESRD patients undergoing hemodialysis in the Arab countries such as Kuwait. Therefore, any generalization of these previous study findings to other hemodialysis patients of different cultures such as ESRD patients in Kuwait is limited due to the different belief systems and self-care practices of these cultures. Thus, the current study aimed to examine the effects of a mindfulness-based intervention on trait mindfulness, perceived stress, emotion regulation, and health-related quality of life in ESRD patients undergoing hemodialysis in Kuwait.

Theoretically, investigating the effects of mindfulness meditation on the selected variables may provide insight into the mechanisms through which mindfulness meditation impacts quality of life in hemodialysis patients. The current study findings may enrich the body of knowledge on mindfulness meditation and bridge the gap in the literature regarding the effects of mindfulness meditation on patients receiving hemodialysis. Practically, the findings of the present study may guide decision-makers in adopting mindfulness meditation in Kuwaiti hospitals.

Methods

Design

This study used a repeated-measures, randomized, wait-list, control design and was conducted between January 2021 and May 2021 in the dialysis center at Jahra Hospital, Kuwait. Seventy-four ESRD patients undergoing hemodialysis were recruited using convenience sampling. Jahra Hospital is a governmental hospital with one of the biggest dialysis centers in Kuwait, with a female ward, male ward, and isolation ward. The center holds 70 dialysis machines/beds, with an average number of 30 patients managed per day.

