The inclusion criteria for participation in this study were being a patient with ESRD undergoing hemodialysis three times a week, being aged 18 years old or over, and being able to read and write in Arabic. The exclusion criteria included being a patient with cognitive dysfunction or mental retardation, taking psychopharmacological drugs, or undergoing psychotherapy. A research assistant, who was not involved in the recruitment or patient assessment processes, randomly assigned the participants to the intervention group (n=37) or the control group (n=37) using a simple 1:1 computer-generated sequence. The trial is reported in accordance with the CONSORT guideline.

Determination of the Sample Size

The required sample size was calculated using G-power version (3.1). Given a mixed-design (within groups and between groups) repeated measures ANOVA, power of 0.95, moderate effect size of 0.25, and α of .0125, the required sample size was 56 subjects. A P-value of 0.0125 was set as the significance level for the main analysis tests. The p-value was adjusted due to multiple testing by dividing the p-value of .05 by 4 (number of dependent variables). In a similar study, an attrition rate of 30% and a non-attendance rate of 30% (excluding dropouts) were estimated (18). Thus, taking into consideration of 60% attrition and nonattendance rates, the final total sample size was 89 patients.

Data Collection Instruments

The study data were collected using an Arabic self-report questionnaire with five parts:

Demographic characteristics. This section included a question for each following variable: Age, gender, employment status, nationality, family status, and educational levels.

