Emotion regulation. Emotion regulation is defined as the processes by which individuals influence which emotions they have and how they experience and express these emotions (24). The Arabic version of the Emotion Regulation Questionnaire (ERQ) was used to assess emotion regulation among the study sample (23). The questionnaire items are scored on a 7-point Likert-type scale ranging from 1 (strongly disagree) to 7 (strongly agree) and are divided into two subscales, namely cognitive reappraisal and expressive suppression. Higher scores indicate greater emotion regulation abilities (24). The Arabic version of the ERQ has shown valid and reliable results among the Arab population (23). In our study, the Chronbach's alpha values for the ERQ was 0.81.

kidney disease-quality of life. The Arabic version of the kidney disease-Quality of Life questionnaire (KDQOL-36) is used to assess kidney disease-related quality of life and consists of four subscales: Generic Core (Physical Component Summary (PCS, 12 items) and Mental Component Summary (MCS, 12 items)); Symptoms/Problems (12 items); Burden of Kidney Disease (4 items), and Effects of Kidney Disease (8 items) (25). The scores of the different subscales are calculated according to the KDQOL-36 scoring system. Raw, pre-coded numeric values for each item are transformed linearly to a range of 0 to 100, with higher scores reflecting better kidney disease-quality of life (26). The Arabic version used in this study showed good psychometric qualities among Arab patients with chronic renal failure (25). In our study, the Chronbach's alpha values for KDQOL-36 was 0.93.

Intervention

The experimental group received the Smith's version of mindfulness meditation (27), which is a standardized theory-based intervention found to be effective in improving stress and its related health problems. The Smith's version of mindfulness meditation (27) comprises the following components:

1. Being mindful of breathing, which includes easily taking in a full, deep breath, filling the lungs, simply exhaling, and then breathing naturally. It also includes noticing and simply attending to the air as it flows in and out of the nose and moves deeper into the throat and lungs (5 minutes).

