First, the permission from the instruments used in the study was obtained. Recruitment of participants was conducted by one of the study researchers after obtaining approval to conduct the study from the hospital administrators. The study purposes and protocol were explained to the patients in detail. Patients who agreed to participate in the study and met the eligibility criteria were asked to sign a consent form, and the participating patients were then randomly assigned to the two study groups. The baseline measurements of the study variables were taken using the self-report questionnaires, which were administered by a research assistant who was not involved in any other parts of the study. The study variables were also measured two weeks post the start of the intervention and at the end of the final session for both groups under the same conditions. All measurements were privately taken at the dialysis center.

Data Analysis

SPSS version 25 (SPSS Inc., Chicago, Illinois, USA) was used to analyze the collected data. Prior to the main analysis, outliers and missing data were examined and managed as appropriate. Then, the assumptions of the statistical tests used, normality using histogram graph, homogeneity of variance, and sphericity were checked and managed as appropriate. Mauchly's test of sphericity is used to assess whether the sphericity assumption has been violated. When Mauchly's test of sphericity was significant ($p < .05$),

the degrees of freedom were corrected using Greenhouse-Geisser estimates of sphericity. The comparability of the two groups was evaluated in terms of demographic characteristics and the baseline measurements of the dependent variables using t-test and Chi square, based on the measurements of the dependent variables. The main analysis was conducted with repeated-measures ANOVA (mixed design: within and between groups). A P-value of 0.0125 was set as the significance level for the main analysis tests. The p-value was adjusted due to multiple testing by dividing the p-value of .05 by 4 (number of dependent variables).

Ethical Considerations

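### Holm at .05 across four tests would keep the 5% family-wise error of the fixed .0125 and never lose power, but one deciding effect and one score per construct must be named first.

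*Combined protocol and SAP*

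**What the plan says.** The aim, at the end of the Introduction, is to "examine the effects of a mindfulness-based intervention on trait mindfulness, perceived stress, emotion regulation, and health-related quality of life", which is four constructs. Data Analysis sets .0125 for the main tests and gives the reason: "The p-value was adjusted due to multiple testing by dividing the p-value of .05 by 4 (number of dependent variables"). Determination of the Sample Size repeats the rule and uses the same level: "repeated measures ANOVA, power of 0.95, moderate effect size of 0.25, and α of .0125, the required sample size was 56 subjects".

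The model is stated in one sentence of Data Analysis: "The main analysis was conducted with repeated-measures ANOVA (mixed design: within and between groups"). No effect within that model is named as the one that decides.

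Data Collection Instruments gives a total-score range for the MAAS (15 to 90) and the PSS (0 to 40). It gives none for the other two instruments. The ERQ items are "divided into two subscales, namely cognitive reappraisal and expressive suppression. Higher scores indicate greater emotion regulation abilities". For the KDQOL-36, "The scores of the different subscales are calculated according to the KDQOL-36 scoring system", and four subscales are listed, or five scores if the physical and mental summaries are counted separately.

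On numbers, Design reports that "Seventy-four ESRD patients undergoing hemodialysis were recruited using convenience sampling". The sample-size section says that "an attrition rate of 30% and a non-attendance rate of 30% (excluding dropouts) were estimated" in a similar study.

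**The concern.** A fixed .0125 ignores what the other three tests show. Once one null hypothesis is rejected, the rest can be tested at a larger level with no loss of family-wise control. Holm does this and the plan does not, so real effects on the second, third or fourth construct can be missed for no benefit in error control.

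The divisor of four is correct only if there are four tests. A mixed ANOVA gives three F tests per score (group, time, group × time), and two of the four constructs have several scores and no stated total. The plan does not say that it will test more than one effect or any subscale. It also does not say which single result decides the claim on emotion regulation or on quality of life. Without that, the count of four cannot be verified and Holm across four tests cannot be carried out.

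**Working it through.** **Inputs from the plan.** Family-wise level .05, four variables, f = 0.25, power 0.95, N = 56, two groups, three measurements (baseline, two weeks after the start, end of the final session), 74 recruited, 30% attrition.

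**Inputs assumed.** The plan gives neither the correlation ρ between repeated measurements (0.3, 0.5 and 0.7 tried) nor the correlation between outcomes (0 and 0.5 tried). Sphericity is assumed unless stated.

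**1. The plan's level.** .05/4 = .0125, as stated. Four tests at .0125 give a family-wise error of at most 4 × .0125 = 5%, or 1 − (1 − .0125)^4 = 4.91% if independent. The guarantee holds with one test per variable.

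**2. The plan's sample size.** For group × time, the noncentrality is λ = f²·N·3/(1 − ρ), with 2 and 2(N − 2) degrees of freedom. At ρ = 0.5 and N = 56, λ = 0.0625 × 56 × 3/0.5 = 21.0, with 2 and 108 df. Power at .0125 is 0.952; at N = 54 it is 0.943. So 56 reproduces at ρ = 0.5. At ρ = 0.3 and 0.7 the required N is 78 and 36, and power at N = 56 is 0.838 and 0.998.

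**3. Which effect fits N = 56.** For the group main effect, λ = f²·N·3/(1 + 2ρ), with 1 and N − 2 df. At N = 56, power is:

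| ρ | 0 | 0.3 | 0.5 | 0.7 |
|---|---|---|---|---|
| Power | 0.742 | 0.496 | 0.393 | 0.321 |

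The time effect does not compare the groups. Of the two effects that do, only group × time is compatible with 95% power at 56.

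**4. Holm's thresholds.** The ordered p-values are compared with .05/4, .05/3, .05/2 and .05, that is .0125, .0167, .025 and .05, stopping at the first failure. None is below .0125, so Holm rejects everything the fixed rule rejects. Single-test power at these levels (N = 56, ρ = 0.5) is 0.952, 0.962, 0.973 and 0.987.

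**5. Simulated gain.** Four interaction F tests, ρ = 0.5, f = 0.25 for each real effect, 40,000 runs. Each cell gives power per real effect at outcome correlation 0 / 0.5.

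| Real effects | N = 56, fixed | N = 56, Holm | N = 52, fixed | N = 52, Holm |
|---|---|---|---|---|
| 4 | 0.952 / 0.952 | 0.985 / 0.981 | 0.934 / 0.934 | 0.978 / 0.972 |
| 3 | 0.952 / 0.953 | 0.972 / 0.971 | 0.933 / 0.934 | 0.961 / 0.956 |
| 2 | 0.954 / 0.951 | 0.963 / 0.960 | 0.933 / 0.935 | 0.946 / 0.945 |
| 1 | 0.951 / 0.951 | 0.951 / 0.951 | 0.934 / 0.933 | 0.934 / 0.933–0.934 |

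N = 52 is 74 × 0.7 = 51.8, rounded. At N = 56 the chance of showing all four rises from 0.823 / 0.860 to 0.946 / 0.953. The chance of at least one finding is identical, because Holm's first threshold is .0125. Simulated family-wise error under Holm with one to four true nulls was 0.043 to 0.050.

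**6. If the count were not four (conditional).** With k tests at .0125 the bound is k × .0125, and the value under independence is 1 − (1 − .0125)^k.

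| Tests made | k | Bound | If independent |
|---|---|---|---|
| MAAS, PSS, 2 ERQ and 4 KDQOL-36 scores | 8 | 10% | 9.6% |
| The same with 5 KDQOL-36 scores | 9 | 11.25% | 10.7% |
| Three ANOVA effects for each of four scores | 12 | 15% | 14.0% |

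For the subscale cases the error falls to about 5% or below at a common score correlation of 0.8 or more (k = 8: 0.047; k = 9: 0.050).

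**The case against.** The strongest reply is that nothing here is an error. The fixed .0125 is valid, is stated consistently and matches the sample-size calculation. That is right: Holm is an efficiency gain. The naming gap affects the present rule just as much, and is arguably the more consequential half.

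The gain also depends on how many patients are analysed. If all 74 were, power per effect at f = 0.25 and ρ = 0.5 is already 0.991 and Holm can raise it only to 0.998. The figure of 52 applies a planning attrition rate from another study, and the number actually analysed is not known. This stands as a limit on size. It is less reassuring if effects are smaller than planned: at N = 74 and f = 0.15 on all four, simulated power per effect rises from 0.62–0.63 to 0.72–0.73.

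The calculations assume sphericity, whereas the plan provides for a Greenhouse-Geisser correction. With ε = 0.75 (assumed), power at N = 56 and .0125 drops from 0.952 to 0.885. This changes the starting point but not the ordering of the two procedures.

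Holm uses more of the permitted error. With three real effects and one true null, its simulated family-wise error is about 4.6–5.1% against 1.1–1.3% for the fixed rule. The 5% guarantee is the same, but the trade should be acknowledged.

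Finally, the single reliability coefficient per instrument and the count of four dependent variables suggest that one score per construct was intended. That is a fair reading, and the inflation figures in step 6 are therefore hypothetical. The score is still not identified for two of the four variables.

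**Conclusion.** The concern holds, as a recommended improvement and not as the correction of an invalid rule. At the same 5% family-wise error, Holm adds about 0.03 to power per effect when all four effects are real at N = 56, 0.02 with three, 0.01 with two and nothing with one. At N = 52 with four real effects the gain is about 0.04. The chance of showing all four rises from 0.82–0.86 to 0.95, though the plan does not make that a criterion.

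These sizes rest on f = 0.25, sphericity, ρ = 0.5 and outcome correlations of 0 to 0.5. At ρ = 0.7 the gain is negligible. At ρ = 0.3, 56 patients would not reach the planned 0.95 under the fixed rule. That Holm is never less powerful depends on none of these assumptions. The absence of a named effect, and of a named ERQ and KDQOL-36 score, is plain from the text and needs closing whichever procedure is used.

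**What to change.** 1. Name group × time as the single deciding effect for each score.
2. Name one confirmatory score per construct: MAAS total, PSS total, one ERQ score and one KDQOL-36 score. Each of the last two may be a subscale, or a total with its formula stated.
3. Replace the fixed .0125 with Holm at family-wise .05 across these four tests, with thresholds .0125, .0167, .025 and .05 and stopping at the first failure.
4. Report the remaining subscales and effects as secondary. If more than four tests are to support claims, apply Holm across all of them.

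N = 56 is unaffected, since Holm's first step is still .0125. The cost is wording only, with no extra patients or measurements. The price is that the other ERQ and KDQOL-36 subscales can no longer carry confirmatory claims.

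Timing matters. The document is dated October 2020 but describes conduct in January to May 2021 and reports in-study reliability coefficients in the past tense. If the data have already been examined, both the choice of scores and the change to Holm are post hoc. In that case keep .0125 for the main result, label Holm a sensitivity analysis, and say when the scores were chosen.
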